### **OPTIONAL INTERIM ANALYSES**

Given the hypothesis-generating nature of this study, the Sponsor may choose to conduct up to two interim analyses. The decision to conduct an optional interim analysis and the timing of the analysis will be documented in the Sponsor's trial master file prior to the conduct of the interim analysis. The interim analysis will be performed by the unmasked internal monitoring committee (IMC) and will be interpreted by the IMC and appropriate senior management personnel. Access to treatment assignment information will follow the Sponsor's standard procedures. The details of the timing and scope of the interim analysis, if any, will be specified in the IMC Agreement.

## **LIST OF ABBREVIATIONS AND DEFINITIONS OF TERMS**

Abbreviation	Definition
ADA	anti-drug antibody
AMD	age-related macular degeneration
anti-VEGF	anti-vascular endothelial growth factor
BCVA	best corrected visual acuity
CARASIL	cerebral autosomal recessive arteriopathy with subcortical infarcts and leukoencephalopathy
CFP	color fundus photograph
CNV	choroidal neovascularization
CRO	contract research organization
DA	disc area
DAP	Data Analysis Plan
EC	Ethics Committee
eCRF	electronic Case Report Form
EDC	electronic data capture
ETDRS	Early Treatment Diabetic Retinopathy Study
FA	fluorescein angiography
FAF	fundus autofluorescence
GA	geographic atrophy
GLP	Good Laboratory Practice
HIPAA	Health Insurance Portability and Accountability Act
HRB	hyper-reflective band
HtrA1	high-temperature requirement A1
ICH	International Council for Harmonisation
IMC	Internal Monitoring Committee
IMP	investigational medicinal product
IND	Investigational New Drug (Application)
IOI	intraocular inflammation
IOP	intraocular pressure
IRB	Institutional Review Board
ITV	intravitreal
IWRS	interactive web-based response systems
LPLV	last patient, last visit
MD	multiple dose
NGS	next-generation sequencing
nAMD	neovascular AMD
NI	near infrared

Abbreviation	Definition
OCT-A	optical coherence tomography angiography
PD	pharmacodynamic
PK	pharmacokinetic
Q4W	every 4 weeks
Q8W	every 8 weeks
RBR	Research Biosample Repository
RPE	retinal pigment epithelium
SAD	single ascending dose
SD-OCT	spectral domain optical coherence tomography
ULN	upper limit of normal
VA	visual acuity
WES	whole exome sequencing
WGS	whole genome sequencing
YAG	yttrium aluminum garnet

## 1. BACKGROUND

## 1.1 BACKGROUND ON GEOGRAPHIC ATROPHY SECONDARY TO AGE-RELATED MACULAR DEGENERATION

Age-related macular degeneration (AMD) is the leading cause of irreversible blindness in people aged 50 years or older in the developed world (Friedman et al. 2004). The majority of the visual loss occurs in the advanced stage of AMD, which has two clinical forms: a non-exudative form, geographic atrophy (GA), which is characterized by loss of photoreceptors, retinal pigment epithelium (RPE), and choriocapillaris; and an exudative or wet form, known as neovascular AMD (nAMD), which is characterized by choroidal neovascularization (CNV) (Sunness et al. 1999; Lindblad et al. 2009). The prevalence of GA increases exponentially with age and approximately quadruples per decade beyond 50 years of age (Rudnicka et al. 2012). The estimated prevalence of GA in populations of European ancestry at 70 years of age is 0.70%, rising to 2.91% at 80 years of age and 11.29% at 90 years of age (Rudnicka et al. 2012).

In the early stages of GA, patients typically show minimal changes in central visual acuity (VA). However, while central VA may not yet be affected, patients often still experience significant symptoms from visual dysfunction, such as dense parafoveal scotomas (e.g., leading to difficulties with face recognition), delayed dark adaptation, reduced contrast sensitivity, and a decrease in reading rate (Sunness et al. 1995, 1999; Sunness and Applegate 1996). In the later stages, as the GA lesion expands into the fovea, a profound decrease in central VA occurs with a decline in activities of daily living (Lindblad and Clemons 2005). Moreover, GA is bilateral in most patients with advanced AMD (Sunness et al. 1999; Lindblad et al. 2009). As such, GA is a significant cause of both moderate and severe central visual loss.

Currently, there are no approved treatments for GA secondary to AMD, and a significant unmet medical need exists for treatment of this serious condition. In Chroma and Spectri, the largest Phase III studies of GA conducted to date, lampalizumab (anti–complement factor D) did not result in a reduction of GA lesion area versus sham during 48 weeks of treatment (Holz et al. 2018). Other more recent Phase II studies have reported positive results: the BEACON study evaluating the brimonidine drug delivery system (Allergan), the FILLY study evaluating APL-2, a synthetic cyclic peptide conjugated to a polyethylene glycol polymer that binds specifically to C3 and C3b (Apellis 2018), and the GATHER1 Study evaluating avacincaptad pegol, an inhibitor of the cleavage of C5 and formation of terminal fragments C5a and C5b (Jaffe et al. 2020).

The Phase II clinical development plan for FHTR2163 (Fab of a humanized monoclonal antibody directed against the high-temperature requirement A1 [HtrA1] protein) is designed to test the safety, tolerability, and efficacy in patients with GA secondary to AMD.

## 1.2 BACKGROUND ON HTRA1

The high-temperature requirement A1 (*HtrA1*) gene, located in chromosomal region 10q26, was one of the first AMD genetic loci identified and has been replicated in multiple studies with associations seen in both linkage and genome-wide association (Weeks et al. 2001; Fritsche et al. 2016). A single nucleotide polymorphism in the promoter region of *HtrA1* is the most likely causal variant, or tags the causal variant, for AMD at 10q26 (DeWan et al. 2006; Yang et al. 2006), and is estimated to confer a population attributable risk of 49.3% (Yang et al. 2006). Transcription of HtrA1 has been shown to be increased in association with the risk allele (Yang et al. 2006).

HtrA1 is a member of the mammalian HtrA serine protease family (Clausen et al. 2002). HtrA1 has been shown to cleave a large number of potential substrates, many of which are extracellular matrix proteins (Grau et al. 2006). In transgenic mice, overexpression of HtrA1 in RPE cells recapitulated cardinal features associated with advanced AMD, including choroidal vasculopathy and severe degeneration of elastic laminae of the Bruch's membrane (Jones et al. 2011; Kumar et al. 2014). At the molecular level, this phenotype appears to result from HtrA1-induced breakdown of extracellular matrix protein associated with RPE, Bruch's membrane, and choroid (Jones et al. 2011; Vierkotten et al. 2011; Kumar et al. 2014). In the human retina, HtrA1 is expressed by RPE cells (DeWan et al. 2006; Yang et al. 2006), and unpublished studies conducted by Genentech revealed that its expression is increased in the area peri-lesional to the GA.

## 1.3 BACKGROUND ON FHTR2163

FHTR2163 (RO7171009) is a Fab of a humanized monoclonal antibody directed against the HtrA1 protein (Tom et al. 2020). FHTR2163 was shown to bind with an equilibrium dissociation constant of 0.13 nM to human HtrA1. The HtrA1 protease is functional only as a trimer. Full inhibition of the enzymatic activity of trimeric HtrA1 requires three separate anti-HtrA1 Fabs to bind each HtrA1 subunit (Ciferri et al. 2015). By inhibiting HtrA1 protease activity, treatment with FHTR2163 may represent a novel therapeutic option for the treatment of GA.

## 1.3.1 FHTR2163 Nonclinical Toxicology Summary

In Good Laboratory Practice (GLP) repeat-dose toxicity studies, FHTR2163 was generally well tolerated in cynomolgus monkeys following bilateral intravitreal (ITV) doses every 2 weeks in studies of up to 6 months in duration at doses of up to 12.5 mg/eye in a 750 mOsm/kg formulation. Hyper-reflective bands (HRBs) were noted on spectral domain optical coherence tomography (SD-OCT) imaging in the fovea of some eyes that were dosed with vehicle or FHTR2163. HRBs were transient, confined to the fovea, and not correlated with functional (full-field electroretinography) or histopathologic abnormalities. These findings suggest that HRBs may be related to the volume and/or number of ITV injections, and are not due to FHTR2163 (Covance Laboratories Inc. report 2018 [available upon request]; Booler et al. 2019). Ocular effects associated with FHTR2163 were limited to ocular inflammation, which was

considered to be procedure related and/or secondary to specific immune-mediated response to a humanized protein. Ocular inflammation was associated with the presence of systemic anti-drug antibodies (ADAs), was not considered to be related to the pharmacologic action of FHTR2163, and showed at least partial reversibility by the end of the 1-month recovery periods. No systemic effects were observed in evaluated parameters, including safety pharmacology endpoints (cardiovascular, respiratory, or behavioral). The no-observed-adverse-effect level in the 6-month GLP repeat–dose toxicity study was considered to be 12.5 mg/eye in a 750 mOsm/kg formulation administered as a single 50-µL ITV injection every 2 weeks.

The toxicology program for FHTR2163 supports both the dose regimens of 20 mg/eye every 4 weeks (Q4W) and every 8 weeks (Q8W), and the duration of this Phase II clinical trial. Refer to the FHTR2163 Investigator's Brochure for details on nonclinical GLP toxicology studies.

# 1.3.2 FHTR2163 Phase I Safety Summary and Pharmacokinetic Preliminary Data

Study GR39821 was an open-label, multicenter, Phase I, first-in-human study designed to investigate the safety, tolerability, pharmacokinetics, and immunogenicity of FHTR2163 administered intravitreally in patients with GA secondary to AMD. The study consisted of two stages: a single ascending dose (SAD) and multiple dose (MD). The SAD stage allowed escalated exposure to FHTR2163 with 5 doses (1, 3, 10, 15, and 20 mg) in 15 patients (3 patients per dose level). The MD stage evaluated the maximum tested dose in SAD (20 mg) administered every 4 weeks for 3 administrations in 10 evaluable patients. The study was completed on 20 November 2018 (last patient, last visit).

In Study GR39821, FHTR2163 was well tolerated. There were no dose-limiting toxicities and no ocular serious adverse events. Two participants, in the MD stage of the study, experienced systemic serious adverse events; none of these events were assessed as related to study drug.

In the SAD cohorts, adverse events reported in >1 participant were as follows: conjunctival hemorrhage (n=5) and conjunctival hyperemia (n=2). In the MD cohorts, adverse events reported in >1 participant were as follows: conjunctival hemorrhage (n=2), conjunctival hyperemia (n=2), skin ulcer (n=2), and squamous cell carcinoma (n=2). None of the systemic or ocular adverse events reported in the SAD or MD cohorts were assessed as related to study drug.

No adverse drug reactions related to FHTR2163 have been identified. Potential risks are discussed in Section 5.1.1.

Based on preliminary pharmacokinetic (PK) analysis, the aqueous humor and serum PK profile of FHTR2163 in humans was generally consistent with other Fabs

(e.g., Lucentis®) administered via ITV injection. The estimated ocular elimination half-life in humans was 4.9 days. The systemic FHTR2163 concentrations following ITV injection are estimated to be at least 7,500-fold lower than vitreal FHTR2163 concentrations.

Based on the results of the Phase I study (GR39821), there has been no change to the potential risks or the reference safety information for FHTR2163 as outlined in the current version of the FHTR2163 Investigator's Brochure.

### 1.4 STUDY RATIONALE AND BENEFIT-RISK ASSESSMENT

As described in Section 1.1, currently, there are no approved treatments to slow or stop the progression of GA secondary to AMD and associated vision loss. FHTR2163 is a first-inclass inhibitor of HtrA1 in clinical development and as such there are no published data on the clinical benefit of this mechanism for the treatment of GA secondary to AMD.

This Phase II study will evaluate the efficacy of FHTR2163 and will further investigate the ocular and systemic safety, tolerability, and pharmacokinetics of FHTR2163 following multiple ITV administrations in patients with GA secondary to AMD.

The clinical experience with FHTR2163 is limited to one first-in-human study (see Section 1.3.2), and the safety profile in humans is not fully understood at this time. The completed nonclinical toxicology studies for FHTR2163 support the continued development of the molecule in clinical studies in patients with GA secondary to AMD (see Section 1.3.1). There are no known risks for FHTR2163 to date. Potential risks are described in Section 5.1.1. Several measures are being taken in this study to mitigate possible safety concerns, including strict inclusion and exclusion criteria (see Section 4.1), regular ocular assessments (see Section 4.5.5), regular ocular imaging (see Section 4.5.6), physical examinations (see Section 4.5.3), and regular safety review by an unmasked Internal Monitoring Committee (IMC) (Section 3.1.2).

Because of the high unmet medical need for new treatments for GA secondary to AMD and the safety profile of FHTR2163 observed in both nonclinical and clinical studies to date, the benefit-risk of FHTR2163 is favorable and supportive of its use in this clinical study.

## 2. OBJECTIVES AND ENDPOINTS

This study will evaluate the safety, tolerability, and efficacy of ITV injections of 20 mg FHTR2163 administered Q4W or Q8W in patients with GA secondary to AMD compared with sham control. Specific objectives and corresponding endpoints for the study are outlined below.

### 2.1 EFFICACY OBJECTIVES

## 2.1.1 Primary Efficacy Objective

The primary efficacy objective for this study is to evaluate the efficacy of ITV injections of 20 mg FHTR2163 administered Q4W or Q8W in patients with GA secondary to AMD compared with sham control on the basis of the following endpoint:

 Mean change in the GA area from baseline to Week 72 as measured by fundus autofluorescence (FAF)

## 2.1.2 Secondary Efficacy Objective

The secondary efficacy objective for this study is to evaluate the efficacy of ITV injections of 20 mg FHTR2163 administered Q4W or Q8W in patients with GA secondary to AMD compared with sham control on the basis of the following endpoints:

- Mean change in best corrected visual acuity (BCVA) score from baseline to Week 72 as assessed by Early Treatment Diabetic Retinopathy Study (ETDRS) chart under low-luminance conditions
- Mean change in BCVA score from baseline to Week 72 as assessed by ETDRS chart

## 2.1.3 Exploratory Efficacy Objectives

The exploratory efficacy objectives for this study are as follows:

- To evaluate the efficacy of ITV injections of 20 mg FHTR2163 administered Q4W or Q8W in patients with GA secondary to AMD compared with sham control on the basis of the following endpoint:
  - Mean rate of change in the GA area, estimated based on GA area as measured by FAF at four timepoints: baseline, Week 24, Week 48, and Week 72
- To evaluate the efficacy of ITV injections of 20 mg FHTR2163 administered Q4W or Q8W in patients with foveal-involving GA and in patients with non-foveal-involving GA compared with sham control on the basis of the following endpoints:
  - Mean change in the GA area from baseline to Week 72 as measured by FAF
  - Mean rate of change in the GA area, estimated based on GA area as measured by FAF at four timepoints: baseline, Week 24, Week 48, and Week 72

### 2.2 SAFETY OBJECTIVE

The safety objective for this study is to evaluate the local and systemic safety and tolerability of ITV injections of 20 mg FHTR2163 administered Q4W or Q8W relative to sham control on the basis of the following endpoints:

 Frequency, severity, and timing of ocular and systemic adverse events, serious adverse events, adverse events leading to study discontinuation, and adverse events of special interest (see Sections 5.2.3 and 5.3.3)

- Frequency, severity, and timing of notable findings in ocular examinations and ocular imaging, including those requiring intervention or start of anti-vascular endothelial growth factor (anti-VEGF) therapy
- Incidence of neovascular AMD diagnosed during the conduct of the study

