### Ocular Exclusion Criteria: Both Eyes

- Active uveitis and/or vitritis (grade trace or above) in either eye
- Active, infectious conjunctivitis, keratitis, scleritis, or endophthalmitis in either eye
- Active or history of ocular melanoma in either eye
- Active or history of CNV in either eye
- Active or history of optic neuritis in either eye
- RPE tear that involves the macula in either eye
- Moderate or severe non-proliferative diabetic retinopathy in either eye

Note: Mild non-proliferative diabetic retinopathy (e.g., occasional hemorrhage or microaneurysm) in either eye may be permitted at the discretion of the investigator. Moreover, a patient with the onset of mild non-proliferative diabetic retinopathy in either eye during study participation may be permitted to continue study treatment at the discretion of the investigator.

- Proliferative diabetic retinopathy in either eye
- Central serous retinopathy in either eye

- Previous participation in an interventional clinical trial for GA or dry AMD trial that tested stem cell treatments, gene therapy, long-acting delivery platforms/formulations (e.g., biodegradable/non-biodegradable implants or formulations, device implant, encapsulated cell technologies), or inhibitors/modulators of the visual cycle (e.g., fenretinide, emixustat) regardless of timing of patient participation
- Previous participation in interventional clinical trials for GA or dry AMD, except for vitamins and minerals, regardless of the route of administration (i.e., ocular or systemic) within the last 6 months

Note: If patient participation in an interventional clinical trial for GA or dry AMD was >6 months prior to screening, the patient may be eligible for the trial at the discretion of the investigator.

- History of recurrent infectious or inflammatory ocular disease in either eye
- History of idiopathic or autoimmune-associated uveitis in either eye

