## 4.2.2 Masking

This is a single-masked study with patients masked to their treatment assignment (study drug vs. sham control). The BCVA examiner will also be masked to the study eye and treatment assigned. The BCVA examiner will only be permitted to perform the refraction, BCVA assessment, and pretreatment IOP measurement. The BCVA examiner will also be masked to the BCVA scores from the patient's previous visits and may only have access to a patient's refraction data from previous visits. Other site study staff will not be masked to the patient treatment assignments.

The central reading center review team, consisting of graders and ophthalmologists experienced in the conduct of clinical trials, will be masked to patients' treatment assignment. They will conduct masked independent review of CFP, FAF, NI, SD-OCT, and OCT-A images to provide an objective assessment of image evaluations.

Contract research organization (CRO) personnel, including clinical research associates, will not be masked to the patient treatment assignments.

Sponsor personnel (except for IMC members) will be masked to treatment assignment until after database lock, unless there is a need to unmask as determined by the IMC. Furthermore, personnel responsible for PK/PD sample management, assays, and analysis may be unmasked as needed (i.e., to evaluate PK relationship to an adverse event). Additionally, for regulatory reporting purposes and if required by local health authorities, the Sponsor will break the treatment code for all serious, unexpected suspected adverse reactions that are considered by the investigator or Sponsor to be related to study drug.

Patients will be masked to HtrA1 risk-variant carrier status.

Patients, site study investigator and staff (study coordinators, etc.), and Sponsor personnel (except for IMC members) will be masked to prebaseline GA growth rate unless there is a need to unmask as determined by the IMC.

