# 5.2.4 Selected Adverse Events

Additional data will be collected for the following selected adverse events:

- Loss of VA ≥30 letters, compared with the last assessment of VA prior to the most recent assessment, lasting more than 1 hour due to study drug treatment
- CNV conversion requiring treatment for either the study eye or non-study eye
- Any clinically significant ocular imaging finding

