# 5.3.1 Adverse Event Reporting Period

Investigators will seek information on adverse events at each patient contact. All adverse events, whether reported by the patient or noted by study personnel, will be recorded in the patient's medical record and on the Adverse Event eCRF.

After informed consent has been obtained but prior to initiation of study drug, only serious adverse events caused by a protocol-mandated intervention (e.g., invasive procedures such as biopsies, discontinuation of medications) should be reported (see Section 5.4.2 for instructions for reporting serious adverse events).

After initiation of study drug, all adverse events will be reported until 28 days after the final dose of study drug. After the 28-day period, only serious adverse events (1) caused by a protocol-mandated intervention (e.g., invasive procedures such as aqueous humor sample), or (2) believed to be related to prior study drug treatment (see Section 5.6) should be reported (see Section 5.4.2 for instructions for reporting serious adverse events).

Instructions for reporting adverse events that occur after the adverse event reporting period are provided in Section 5.6.

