# 5.3.5.3 Abnormal Findings on Ocular Imaging

Not every abnormal imaging finding on ocular imaging qualifies as an adverse event. An abnormal finding on ocular imaging must be reported as an adverse event if it meets any of the following criteria:

- Is accompanied by clinical symptoms
- Results in a change in study treatment (e.g., dosage modification, treatment interruption, or treatment discontinuation)
- Results in a medical intervention or a change in concomitant therapy
- Is clinically significant in the investigator's judgment

It is the investigator's responsibility to review all ocular images. Medical and scientific judgment should be exercised in deciding whether an isolated imaging abnormality should be classified as an adverse event.

If a clinically significant abnormal image finding is a sign of a disease or syndrome (e.g., retinal edema), only the diagnosis (i.e., CNV) should be recorded on the Adverse Event eCRF.

Observations of the same clinically significant abnormal image finding from visit to visit should only be recorded once on the Adverse Event eCRF (see Section 5.3.5.6 for details on recording persistent adverse events).

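### Late neovascular AMD can go unrecorded: general adverse event recording ends 28 days after the last dose, before the Week 72 imaging in the Q8W arms

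*Combined protocol and SAP*

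**What the plan says.** **Endpoint.** Section 2.2, repeated in the synopsis, lists "Incidence of neovascular AMD diagnosed during the conduct of the study". It names no eye, diagnostic source, criterion or closing date. Section 6.5 adds only descriptive summaries. Section 5.2.4 collects extra data on a narrower event, "CNV conversion requiring treatment for either the study eye or non-study eye". Both eyes start free of the condition, because "Active or history of CNV in either eye" is an exclusion.

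**Who diagnoses and where it is recorded.** Section 5.3.5.3 states "It is the investigator's responsibility to review all ocular images" and, where an image finding is a sign of disease, "only the diagnosis (i.e., CNV) should be recorded on the Adverse Event eCRF". Section 4.2.2 masks the BCVA examiner and then says "Other site study staff will not be masked to the patient treatment assignments". The same section describes masked readers at the central reading center: "They will conduct masked independent review of CFP, FAF, NI, SD-OCT, and OCT-A images to provide an objective assessment of image evaluations". No visible text links that reading to this endpoint.

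**When recording stops.** Under Section 5.3.1, "all adverse events will be reported until 28 days after the final dose of study drug". After that, only serious events caused by a protocol-mandated intervention, or thought related to earlier study drug, are to be reported. Footnote aa in both schedules and Section 5.6 repeat this. Section 5.4.2.2, by contrast, keeps serious events and events of special interest reportable to Week 76 with no relatedness condition. The adverse event rows in both schedules are marked at Weeks 72 and 76.

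**Dosing and imaging.** Treatment ends at Week 68 on Q4W and Week 64 on Q8W (Section 3.1). Week 72 has the only scheduled color fundus photograph after baseline and the last scheduled SD-OCT and OCT-A (Appendices 1 and 2).

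**The concern.** The endpoint runs for the whole study, but the form on which the plan describes a diagnosis being entered is tied to the last dose. The last dose differs by schedule, and it comes much earlier in patients who stop treatment and are encouraged to keep attending (Sections 3.1 and 4.6.1). The most informative imaging visit then falls outside the recording period for some groups and inside it for others.

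Conversion to neovascular AMD is the one disease-specific outcome named among the safety endpoints. If late cases are counted by different rules in different groups, the comparison with sham carries a difference that has nothing to do with the drug. Early stopping need not be balanced either: ocular inflammation is a listed risk of the drug with its own discontinuation criteria (Section 5.1.1.1). The site investigator, who knows the treatment, also decides whether a late finding is serious, drug-related or sight-threatening, and so whether it passes the day-28 limit.

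**Working it through.** **Inputs from the plan**
- Last treatment at Week 68 (Q4W) and Week 64 (Q8W); 18 and 9 treatments (Section 3.1).
- Recording limit of 28 days, or 4 weeks, after the final dose (Section 5.3.1).
- Visit windows of ±5 days; SD-OCT every 8 weeks to Week 72; on Q8W no scheduled visit between Weeks 64 and 72 (Appendices 1 and 2).
- Planned allocation: 144 drug Q4W, 72 drug Q8W, 72 sham Q4W, 72 sham Q8W.

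**Assumptions not in the plan.** Constant hazard over 72 weeks, equal in all arms; visit days independent and uniform within their windows; sham pooled for safety; conversion risk of 2% to 10%. The shares below apply only to events bound by the 28-day rule.

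**1. Plan's own figures.** Weeks 0 to 68 by 4: 68/4 + 1 = 18 treatments. Weeks 0 to 64 by 8: 64/8 + 1 = 9 treatments. Both match.

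**2. Closing week.** Q4W: 68 + 4 = Week 72. Q8W: 64 + 4 = Week 68.

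**3. Days from last dose to the Week 72 visit.** Q8W: 56 ± 10 = 46 to 66 days, always past day 28. Q4W: 28 ± 10 = 18 to 38 days. Of 11 × 11 = 121 pairs of visit days, 11 give exactly 28 and the other 110 split evenly, so 55/121 = 45% fall past day 28.

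**4. Share of conversions counted in completers.** Two readings bracket the effect: onset dated exactly, or a conversion counted only when first seen at a scheduled visit.

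| Reading | Q4W | Q8W | Pooled sham | Q4W / sham | Q8W / sham |
|---|---|---|---|---|---|
| Exact onset | 72/72 = 1.000 | 68/72 = 0.944 | 0.972 | 1.029 | 0.971 |
| First seen at visit | 72/72 = 1.000 | 64/72 = 0.889 | 0.944 | 1.059 | 0.941 |

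With no drug effect every ratio should be 1. The distortion is about 3% to 6%.

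**5. Effect of visit windows.** The table takes Q4W as fully covered. If 45% of Q4W Week 72 visits are also late, and cases arising in Weeks 64 to 72 are seen only on the Week 72 SD-OCT, the Q4W share is 1 − (55/121)(8/72) = 0.949. Pooled sham is then (0.949 + 0.889)/2 = 0.919. The ratios become 0.949/0.919 = 1.03 and 0.889/0.919 = 0.97.

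**6. In cases.** At an assumed 5% risk the Q8W drug arm expects 72 × 0.05 = 3.6 cases. It loses 3.6 × 4/72 = 0.2 to 3.6 × 8/72 = 0.4. At 2% the loss is 0.08 to 0.16 of 1.44; at 10% it is 0.4 to 0.8 of 7.2.

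**7. Early stop.** For a last dose at week s, the uncovered fraction is (72 − s − 4)/72. With s = 24 it is 44/72 = 61%. The plan does not say how many such patients to expect.

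**8. The rules side by side for a conversion first seen at Week 72 on Q8W.** Sections 5.3.1 and 5.6 and footnote aa admit it only if serious and either drug-related or procedure-related. Section 5.4.2.2 admits it if serious or of special interest, whatever the cause. The schedule row asks for adverse events at that visit. These instructions cannot all be followed.

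**The case against.** The strongest reply is that the form does not simply close. Section 5.2.3 makes an event sight-threatening, and so serious, if the investigator thinks it may need medical treatment to avert lasting visual loss. Much neovascular AMD needing treatment could qualify and be reported to Week 76 under Section 5.4.2.2. Concomitant medications and ocular procedures in both eyes are also recorded to Week 76, so anti-VEGF treatment would be visible. After the Week 64 dose on Q8W there is a safety call at 14 ± 5 days, and unscheduled imaging is possible. Safety is descriptive, and Q8W drug against Q8W sham has identical windows in completers.

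Most of this stands, and it confines the gap to late conversions not reported as serious or of special interest. It does not close the gap. The sight-threatening route depends on an unmasked opinion. Sections 5.3.1 and 5.6 contradict the Week 76 rule by requiring a relation to drug or procedure, which would seldom be claimed for the drug in a sham patient.

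Two stronger readings are tempting and not supported:
- **That the endpoint rests on unmasked site diagnoses.** The source is unspecified. Ocular imaging is listed separately among the safety summaries in Section 6.5, masked reading exists, and Section 5.3.5.3 is a recording rule that does not define the endpoint.
- **That either eye counts, so the untreated eye dilutes the result.** Section 2.2 is silent on the eye. Dilution needs a merged count. At an assumed 5% per eye and a study-eye risk ratio of 2, merging gives (1 − 0.90 × 0.95)/(1 − 0.95²) = 0.145/0.0975 = 1.49. The risk difference barely moves, from 5.0 to 4.75 points.

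**Conclusion.** The concern holds as a timing and recording defect. The endpoint covers the whole study, while the general recording rule that would supply it stops at Week 68 on Q8W, nominally at Week 72 on Q4W, and earlier still after an early treatment stop. The reporting sections and the schedules contradict each other on what happens next.

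For completers the consequence is small: about 3% to 6% against pooled sham, or a fraction of one case in the Q8W drug arm. This rests on constant hazard and on pooling sham for safety, which the plan states for efficacy but not in Section 6.5. For patients who stop treatment and stay, the individual loss is much larger. Its effect on the comparison depends on how many stop and in which arm, which the documents do not give.

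The Data Analysis Plan, Table 1 and part of the ocular-risk text were not available. A definition there could settle the eye and the source. The conflict among the visible sections would still need reconciling.

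**What to change.** 1. In Section 2.2 and the synopsis, define the endpoint as new neovascular AMD through the last study visit (Week 76) in all arms, whatever the time since the last dose. Report study eye and non-study eye separately.
2. Name the masked central reading of scheduled SD-OCT, color fundus photographs and, where done, OCT-A as the confirming source. Show investigator diagnoses alongside.
3. Reconcile Sections 5.3.1, 5.4.2.2 and 5.6, footnote aa, and the adverse event rows at Weeks 72 and 76, so that a site has one instruction for recording new CNV in any patient still being followed.

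With a common cut-off, the no-effect ratio returns to 1.00 for every comparison among completers, and patients who stop early contribute for as long as they attend.

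The cost is revised endpoint wording and an eCRF completion note. The reading center may need to add a CNV field, since no visible text says it grades CNV; the images are already taken and sent to it. OCT-A is available only at some sites, and the central and investigator counts may differ, so both must be shown and explained.
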